8.8. Summary of Reasons for Efficacy Non-Evaluability/Exclusion from Efficacy Analyses

The reasons for excluding subjects from the PPS will be listed by treatment and subject.

9. SAFETY AND TOLERABILITY

9.1. Overall Summary of Tolerability

The safety analyses will be based on the SAS, unless otherwise specified. If a subject is randomized in the study more than one time, it will be decided at the Blind Data Review Meeting (BDRM) or after unblinding, on a case by case basis if the subject is counted in the numerator of any specific safety analysis.

Table 6 provides an overview of the planned analyses.

Table 6: Overview of Planned Safety Analyses

Display Type	Data Displays Generated		
	Table	Figure	Listing
Adverse Events			
Overview	Y[2]		
Treatment Emergent AEs	Y[1][2]		Y
Treatment Emergent AEs Severity	Y[2]		Y
Treatment-Related Emergent AEs	Y[2]		Y
Placebo Run-In Period AEs	Y[2]		Y
Pre-run-in period AEs			Y
AEs Leading to Withdrawal			Y
SAEs	Y[2]		Y
Treatment Emergent SAEs	Y[2]		Y
Treatment Emergent SAEs Severity	Y[2]		Y
Treatment-Related Emergent SAEs	Y[2]		
Laboratory			
Pregnancy Test Results			Y
Other			
Vital Signs	Y[3] [2]		Y
Physical Examination	Y[4] [2]		Y
Focused ENT Examination	Y[5] [2]		Y

NOTES :

- Y = Yes display generated.
- [1]: Display will also be produced by SOC, severity, and by relationship to study medication
- [2]: Display will be based on safety analysis set
- [3]: Display will be produced separately for overall summary (inc. change from baseline), for potentially clinically significant results, and shift tables
- [4]: Display will be produced separately for overall summary
- [5]: Display will be produced separately for overall summary and for potentially clinically significant results

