6.5.2. Full Analysis Set (FAS)

The FAS will consist of all subjects who are randomized and received at least one dose of investigational product and have at least one post-baseline primary efficacy assessment. If a subject is randomized in the study more than one time, it will be decided at the Blind Data Review Meeting (BDRM) on a case by case basis if the subject should be included in FAS. Full analysis set will be the primary analysis set for efficacy analyses.

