6.5.4. Safety Analysis Set (SAS)

The Safety Analysis Set (SAS) will consist of all subjects who are randomized and receive at least one dose of study medication following randomization and will be used for all safety analyses.

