6.6. Baseline Definition

Unless otherwise specified, the following general principles apply for determining the baseline for daily diary variables and for variables collected during scheduled visits:

Primary endpoint parameter rTNSS

The baseline will be defined as the average of the last 8 consecutive AM and PM assessments during the last 4 days of the run-in period from the Day -4 PM assessment to the AM assessment on the day of randomization. At least 6 out of 8 reading scores should be available in order to calculate baseline score.

Secondary and other 12-hour average AM and PM endpoint parameters

The same method will be used to determine the baseline for secondary and other 12-hour average AM and PM efficacy endpoint parameters:

- average AM and PM rTNSS, iTNSS, and corresponding AM and PM individual symptoms
- average AM and PM rTOSS; average AM and PM iTOSS
- average AM and PM rTNNSS, average AM and PM iTNNSS and corresponding individual symptoms

Other endpoints for AM or PM nasal/non-nasal symptoms

The baseline score will be defined as the average of the last 4 consecutive AM or PM assessments (respectively for either AM or PM corresponding endpoint) during the last 4 days of the run-in period from the Day -4 PM assessment to the AM assessment on the day of randomization. At least 3 out of 4 reading scores should be available in order to calculate baseline score.

Safety endpoints

Unless otherwise specified, 'baseline' for safety analysis will be defined as the last available assessment prior to the first dose of study drug following randomization.

PRQLQ and PNSS

Baseline is defined as the score at the Randomization Visit (Day 1; Visit 2).

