9.2. Adverse Event Preferred Term and Body/Organ System Summary Tables

9.2.1. Summaries of Adverse Event Incidence Rates for All Subjects

Adverse events will be coded using Medical Dictionary for Regulatory Activities (MedDRA) version 21.0.

All AEs will be displayed in listings.

Any AE that occurs during the placebo run-in period will be summarized separately from the AEs occurring during the randomized treatment period. Any AE that occurs pre-run-in (between the subjects signing informed consent and administration of the first dose of the run-in study medication) will be listed. Adverse events occurring after the first dose of the randomized study medication will be defined as treatment-emergent adverse events (TEAEs).

A comparison of the incidence rate of AEs between study treatment groups will be presented overall, occurring in greater or equal to 1%, 2%, 3%, as well as AEs occurring in the study treatment arm in higher frequency than in placebo arm. Incidence rate is determined by the number of subjects with AEs divided by the total duration (day) of treatment across all subjects in given treatment group, multiplied by 100.

Summaries of the number of subjects with TEAEs and the number of TEAEs experienced will be presented by treatment. The number of subjects and the number of TEAEs will be presented using frequency counts and percentages, overall and by system organ class (SOC) and preferred term (PT). The percentages will be calculated as the number of subjects with TEAEs divided by the number of subjects in each treatment in the safety analysis set. Tables of the number and percentage of subjects and the number of TEAEs by intensity and by relationship to study medication will also be presented. If severity of an event is missing, then set AE severity as "Severe". If relationship to study treatment is missing, then set relationship as "Related". Similar tables will be created for treatment related emergent AEs (TREAEs). Events will be assigned to the study treatment administered prior to the start of the TEAE. Events that occurred during discharge and final follow-up will be assigned to the study treatment administered prior to the start of the event.

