9.6. Vital Signs

The subject's post-baseline vital signs will be recorded (pulse rates, sitting systolic and diastolic blood pressure) at Visits 3 and 4. Height and weight will also be recorded at Visit 4. Descriptive statistics (number of subjects, mean, standard deviation, median, minimum and maximum) will be used to summarize vital sign results and changes from baseline by treatment group and visit.

Values outside the respective normal range and values deemed as clinically significant by the Investigator will be listed. Normal ranges for pulse rate, systolic BP and diastolic BP are listed in Table 7.

Table 7: Normal ranges of vital signs ^{6,7}

Vital Sign	Abnormal Criteria
Pulse Rate (Beats/min)	Pulse rate: 6-11 years and Result is <60 or >95
Systolic BP (mmHG)	Systolic BP: 6-9 years and Result is <95 or >110 Systolic BP: 10-11 years and Result is <100 or >119
Diastolic BP(mmHG)	Diastolic BP: 6-9 years and Result is <60 or >73 Diastolic BP: 10-11 years and Result is <65 or >76

The number of subjects with values of potential clinical significance determined by the investigator will be tabulated by treatment group and visit.

All vital sign data will be listed by treatment and subject.

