	Placebo NS (N=xxx)	GSP 301 NS (N=xxx)	Total (N=xxx)
Number of subjects with at least 1 protocol deviation	xxx (xx.x)	xxx (xx.x)	xxx (xx.x)
Total deviations	xxx	xxx	xxx
Concomitant medication	xxx (xx.x)	xxx (xx.x)	xxx (xx.x)
Exclusion criteria	xxx (xx.x)	xxx (xx.x)	xxx (xx.x)
Inclusion criteria	xxx (xx.x)	xxx (xx.x)	xxx (xx.x)
Informed consent	xxx (xx.x)	xxx (xx.x)	xxx (xx.x)
Study treatment compliance	xxx (xx.x)	xxx (xx.x)	xxx (xx.x)
Study treatment randomization	xxx (xx.x)	xxx (xx.x)	xxx (xx.x)
Investigator record keeping source docs	xxx (xx.x)	xxx (xx.x)	xxx (xx.x)
Study treatment administration/dispense	xxx (xx.x)	xxx (xx.x)	xxx (xx.x)
Visit scheduling	xxx (xx.x)	xxx (xx.x)	xxx (xx.x)
Did not Satisfy Inclusion/Exclusion That May Have Significant Influence on Efficacy	xxx (xx.x)	xxx (xx.x)	xxx (xx.x)
Not Treated with Treatment Assigned at Randomization, but Wrongly Treated in Another Treatment Group	xxx (xx.x)	xxx (xx.x)	xxx (xx.x)
Other Major Deviations	xxx (xx.x)	xxx (xx.x)	xxx (xx.x)

Source: Listing 16.2.2.1

N=Number of subjects in SAS; percentages are based on N.

The same subject may have had more than 1 major protocol deviation.

Program: xxxx.sas Executed: DDMMYY YYYY HH:MM

Page X of Y

Programming Notes:

1. Need to verify protocol deviations (all "Major" from the BDRM spreadsheet) regardless of the study period for the SAS subjects.
2. If a category above has no data in any of the columns, do not display. New categories might be added at BDRM review.

Table 14.1.3.1 Summary of Analysis Populations

	Placebo NS (N=xxx)	GSP 301 NS (N=xxx)	Number (%) of subjects Total (N=xxx)
Run-in Set			xxx
Randomized	xxx	xxx	xxx
Not treated as randomized	xxx (xx.x)	xxx (xx.x)	xxx (xx.x)
Did not receive any study medication [a] following randomization	xxx (xx.x)	xxx (xx.x)	xxx (xx.x)
Safety analysis set	xxx (xx.x)	xxx (xx.x)	xxx (xx.x)
Full analysis set	xxx (xx.x)	xxx (xx.x)	xxx (xx.x)
Randomized but excluded from FAS	xxx (xx.x)	xxx (xx.x)	xxx (xx.x)
Did not receive at least one dose of study medication	xxx (xx.x)	xxx (xx.x)	xxx (xx.x)
Did not have at least one post-baseline primary efficacy Assessment	xxx (xx.x)	xxx (xx.x)	xxx (xx.x)
Randomized twice in the same study [b]	xxx (xx.x)	xxx (xx.x)	xxx (xx.x)
Per protocol set	xxx (xx.x)	xxx (xx.x)	xxx (xx.x)
Randomized but excluded from PP due to major protocol deviation	xxx (xx.x)	xxx (xx.x)	xxx (xx.x)

Source: Listing 16.2.1.1, 16.2.3.1, 16.2.3.2

N=Number of subjects randomized; percentages are based on N.

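### Minor: SAP 9.1 lets the choice of whether a subject randomised more than once counts in a safety numerator be made after unblinding, whereas SAP 6.5.2 keeps the FAS decision for such subjects at the blinded meeting

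*SAP*

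**What the plan says.** SAP 9.1 deals with a subject who is randomised more than once. One option is to decide at the Blind Data Review Meeting (BDRM). The text then adds the alternative: "or after unblinding, on a case by case basis if the subject is counted in the numerator of any specific safety analysis". SAP 5.2 places unblinding after database lock, so a decision taken at that stage is made with both treatment and events known.

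SAP 6.5.2 deals with the same trigger for the Full Analysis Set: "it will be decided at the Blind Data Review Meeting (BDRM) on a case by case basis if the subject should be included in FAS". No later option is given there.

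The rules that produce the adverse event percentages are elsewhere:

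- The Safety Analysis Set (SAP 6.5.4) "will consist of all subjects who are randomized and receive at least one dose of study medication following randomization". It has no provision for a second randomisation.
- SAP 9.2.1 attributes events by treatment taken: "Events will be assigned to the study treatment administered prior to the start of the TEAE".
- SAP 9.2.1 defines the percentage as "the number of subjects with TEAEs divided by the number of subjects in each treatment in the safety analysis set".

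The situation is foreseen. Shell Table 14.1.3.1 has a row for subjects randomised twice. Its footnote is left to be written for each case, with a note that the row may turn out not to be needed.

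**The concern.** Safety and tolerability are the secondary objective of a double-blind trial. Section 9.1 permits a counting choice that may be made with treatment known, may differ from one safety table to the next, and is tied to no stated criterion. Elsewhere the plan settles comparable choices earlier: FAS inclusion at the BDRM (SAP 6.5.2), major deviations at the BDRM before lock (SAP 6.5.3), and allocation to analysis sets before hard-lock (Protocol 13.2).

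A second feature is that 9.1 mentions the numerator only. A dosed child whose event is not counted is still a member of the Safety Analysis Set and so stays in the denominator. Leaving such a child out of the numerator alone can only lower the percentage for that arm.

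What is at stake is a summary percentage, or whether a term appears in one of the cut-off tables. No efficacy result is affected.

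**Working it through.** **1. The two rules side by side**

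| | SAP 6.5.2 (FAS) | SAP 9.1 (safety) |
|---|---|---|
| Trigger | Randomised more than once | Randomised more than once |
| What is decided | Membership of the set | Counting in a numerator |
| When | BDRM | BDRM or after unblinding |
| Scope | One decision | Any specific safety analysis |
| Criterion | None | None |

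The lack of a criterion is common to both. The option to decide after unblinding is found only in 9.1, as is the explicit table-by-table scope.

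**2. What the other rules already settle**

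SAP 9.2.1 says which treatment an event belongs to. Footnote [a] of shell Table 14.3.1.1 and the footnote to Table 14.3.1.2 say that a subject with several events is counted once at each level. Together these settle most of the counting. Two things stay open: the discretion in 9.1 to leave the subject out altogether, and the denominator when both treatments were received.

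**3. Size of one child**

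Inputs: SAP 4.3.1 gives 382 evaluable, 15% drop-out and about 450 randomised, 225 per group. The plan's own figure reproduces: 382 / (1 − 0.15) = 449.4, rounded up to 450, and 450 / 2 = 225. I assume that all 225 per arm are dosed and that there is one such child.

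- One child: 1 / 225 = 0.44 percentage points.
- A term seen in three children: 3 / 225 = 1.33% if the child is counted.
- Left out of the numerator only: 2 / 225 = 0.889%.
- Left out of numerator and denominator: 2 / 224 = 0.893%.

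The last two differ by 0.004 points. The numerical effect therefore comes from whether the child is counted, and hardly at all from the denominator mismatch.

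**4. Table cut-offs**

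The smallest count that reaches each cut-off at 225 is the first whole number at or above 2.25, 4.5 and 6.75.

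| Cut-off | Smallest count reaching it | One fewer |
|---|---|---|
| 1% | 3 / 225 = 1.33% | 2 / 225 = 0.89% |
| 2% | 5 / 225 = 2.22% | 4 / 225 = 1.78% |
| 3% | 7 / 225 = 3.11% | 6 / 225 = 2.67% |

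One child can therefore carry a term across a cut-off, but only if the term sits exactly at the boundary. The shells do not say which arm's frequency triggers inclusion. If either arm suffices, the term must also be below the cut-off in the other arm.

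**The case against.** The strongest reply is practical. The protocol describes no route to a second randomisation. Section 12.1 allows one re-screening for a Visit 1 failure and bars it once run-in has begun, and Section 7.4.3 rules out replacement. Safety is descriptive and all adverse events are listed. A term that drops out of a cut-off table still appears in the uncut Table 14.3.1.2 if any other child had it. All of this stands, and it is why the point is minor.

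A second reply is that the two sections do not decide the same thing. One fixes membership of the set used for the primary test; the other fixes counting in descriptive tables. That is also correct. The contrast is limited to timing for the same type of subject, and it does not show that 6.5.2 is a complete rule.

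A third reply is that, while the study is blinded, nobody knows whether a child randomised twice received one treatment or both, so the option may have been added for that reason. The reason is plausible, but it does not justify the wording. Knowledge of treatment is needed to apply a counting rule, not to choose one.

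A reader might infer more than the documents support:

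- That the decision will be made unblinded. The text makes this an alternative, and names the BDRM first.
- That 9.1 breaches Protocol 13.2. That section concerns allocation to analysis sets, and 9.1 does not change set membership.
- That the same defect runs through the safety baseline, the examination tables and exposure. Those sections do not involve unblinding, and a problem there requires both randomisations to be held under one subject record, which the documents do not say.

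**Conclusion.** The point holds as a minor one. SAP 9.1 permits a treatment-aware, table-by-table choice on numerator counting, where SAP 6.5.2 keeps the FAS decision for such subjects at the BDRM. Both lack a criterion, so the inconsistency is in timing. A child left out of a numerator under 9.1 would remain in the denominator.

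The documents give no frequency for such children; from the re-screening and replacement rules I expect it to be near zero. If there were one, the effect would be 0.44 percentage points, with a possible move across a 1%, 2% or 3% cut-off. This assumes 225 dosed per arm and a term at the boundary. The documents do not support a claim that the safety conclusions are at material risk. The reason to act is that the discretion is avoidable at almost no cost.

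**What to change.** In SAP 9.1, delete the words *or after unblinding*, have such subjects identified at the BDRM, and state before database lock one rule for all safety event tables. For example:

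> Each TEAE, as defined in Section 9.2.1, is assigned to the study treatment administered before its onset. A subject randomised more than once counts once in the denominator of each arm whose double-blind treatment was received, and once in that arm's numerator if an event is assigned to it.

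Other rules would serve equally well if fixed at the same time. Whichever is chosen should leave the existing TEAE definition in 9.2.1 untouched. The rule is chosen while blinded and applied after unblinding with no further decision.

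The cost is SAP wording. If one subject received both treatments, the two arm denominators add up to one more than the number of unique subjects, which needs a footnote.

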9.2. Adverse Event Preferred Term and Body/Organ System Summary Tables

9.2.1. Summaries of Adverse Event Incidence Rates for All Subjects

Adverse events will be coded using Medical Dictionary for Regulatory Activities (MedDRA) version 21.0.

All AEs will be displayed in listings.

Any AE that occurs during the placebo run-in period will be summarized separately from the AEs occurring during the randomized treatment period. Any AE that occurs pre-run-in (between the subjects signing informed consent and administration of the first dose of the run-in study medication) will be listed. Adverse events occurring after the first dose of the randomized study medication will be defined as treatment-emergent adverse events (TEAEs).

A comparison of the incidence rate of AEs between study treatment groups will be presented overall, occurring in greater or equal to 1%, 2%, 3%, as well as AEs occurring in the study treatment arm in higher frequency than in placebo arm. Incidence rate is determined by the number of subjects with AEs divided by the total duration (day) of treatment across all subjects in given treatment group, multiplied by 100.

Summaries of the number of subjects with TEAEs and the number of TEAEs experienced will be presented by treatment. The number of subjects and the number of TEAEs will be presented using frequency counts and percentages, overall and by system organ class (SOC) and preferred term (PT). The percentages will be calculated as the number of subjects with TEAEs divided by the number of subjects in each treatment in the safety analysis set. Tables of the number and percentage of subjects and the number of TEAEs by intensity and by relationship to study medication will also be presented. If severity of an event is missing, then set AE severity as "Severe". If relationship to study treatment is missing, then set relationship as "Related". Similar tables will be created for treatment related emergent AEs (TREAEs). Events will be assigned to the study treatment administered prior to the start of the TEAE. Events that occurred during discharge and final follow-up will be assigned to the study treatment administered prior to the start of the event.

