6. INVESTIGATIONAL PLAN

6.1. Overall Study Design

This is phase 3, double-blind, randomized, parallel-group, placebo-controlled study conducted in multiple centers in the US. All study sites will enroll subjects during the spring or fall allergy season, as applicable. The study will evaluate the efficacy and safety of GSP 301 NS administered as [redacted] spray/nostril [redacted] compared with placebo NS in the same vehicle in pediatric subjects with SAR.

Subjects will be randomized to treatment in a 1:1 ratio to the following 2 treatment groups:

- GSP 301 NS [redacted] µg olopatadine HCl [redacted] µg mometasone furoate administered as [redacted] spray/nostril BID in the AM and PM).
- Placebo NS (administered as [redacted] spray/nostril [redacted] in the AM and PM).

This study consists of 4 visits to the study site (Figure 1). After the initial Screening Visit (Visit 1), subjects (aged ≥ 6 to <12 years) with SAR who meet all study selection criteria will undergo a single-blind, placebo run-in period for 7 to 10 days. Following the completion of the placebo run-in period, eligible subjects meeting the randomization criteria will be randomized to 1 of the 2 treatment groups. Randomized subjects will undergo a 2-week (14-day) treatment period to assess the efficacy and safety of the assigned treatment. The end of the study will be the date of the last study visit for the last subject in the study.

Pollen counts will be obtained each weekday, and when possible, each weekend day at each investigational site, either by study staff or by a community counting station located within approximately 30 miles of the study site. Three (3) consecutive days of moderate pollen counts will be accepted as the start to that pollen's given allergy season. The definition of 'moderate' varies depending on the allergen. Guidelines for identifying a moderate range can be found at <http://www.aaaai.org/global/nab-pollen-counts/reading-the-charts.aspx> or local guidelines can be used. However, the first subject should be screened only after meeting the moderate pollen count criteria for that relevant pollen season and upon consultation with the Sponsor's study team and approval. Pollen counts will be entered as part of the data entry in the case report forms/electronic case report forms (CRFs/eCRFs) or other methods as provided by the Sponsor or designee.

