11.2.1. Adverse Event

An AE is defined as any untoward medical occurrence in a subject administered study drug that does not necessarily have a causal relationship with the treatment. An AE can, therefore, be any unfavorable and unintended sign (including an abnormal laboratory finding), symptom or disease (new or exacerbated) temporally associated with the use of the study drug, whether or not related to the study drug. An AE includes any event, regardless of the presumed causality between the event and the study drug.

Events that, while not necessarily meeting the definition of AEs, should be treated as such because they may be reportable to Regulatory Authorities according to AE reporting regulations, whether or not considered causally associated with IP, include the following:

- Study drug overdose, whether accidental or intentional
- Study drug abuse
- An event occurring from study drug withdrawal
- Any failure of expected pharmacological action
- Inadvertent or accidental study drug exposure (eg, product leaking or being spilled onto a subject or care-giver)
- Unexpected therapeutic or clinical benefit from the study drug
- Medication errors (ie, incorrect route of administration, incorrect dosage, use of incorrect product).

Events that do not meet the definition of an AE include:

- Medical or surgical procedure (eg, endoscopy, appendectomy); the condition that leads to the procedure is an AE
- Situations where an untoward medical occurrence did not occur (social and/or convenience admission to a hospital)
- Anticipated day-to-day fluctuations of pre-existing disease(s) or condition(s) present or detected at the start of the study that do not worsen
- The disease/disorder being studied or expected progression, signs, or symptoms of the disease/disorder being studied, unless more severe than expected for the subject's condition.

Note that significant worsening of symptoms (ie, requiring systemic steroids, antibiotics, or hospitalization) will be reported as an AE.

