13.8.3. Adverse Events, Concomitant Medications, and Withdrawals

All AEs will be coded according to the current version of Medical Dictionary for Regulatory Activities, version 19 or higher. Adverse events occurring between the signing of informed consent and administration of the first dose (randomized treatment) of study medication will be regarded as pre-treatment AEs and included in the subject listings but not in the summary tables. Adverse events occurring after the first dose of study medication will be defined as TEAEs and will be listed and summarized by SOC and PT.

Summaries of the number of subjects with TEAEs and the number of TEAEs experienced will be presented by treatment. The number of subjects and the number of TEAEs will be presented using frequency counts and percentages, overall and by SOC and PT. Tables of the number and percentage of subjects and the number of TEAEs by intensity and by relationship to study medication will also be presented. Events will be assigned to the study drug administered prior to the start of the TEAE. Events that occurred during the study discontinuation visit and final follow-up will be assigned to the final treatment.

Details of SAEs and AEs leading to withdrawal of the subject from the study will also be presented by treatment group. Withdrawals from the study, and associated details, will be presented by treatment group. Any withdrawals will be listed and summarized by reason for withdrawal, treatment and by any other relevant categorical information.

Concomitant medications will be listed.

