Repeat table 14.3.1.2 for Treatment-Emergent Adverse Events with frequency $\geq 3\%$

Table 14.3.1. 14 Summary of Treatment-Emergent Adverse Events with frequency higher in GSP 301 NS group than in Placebo NS group (Safety Analysis Set)

Source: Listing 16.2.7.1, 16.2.7.2, 16.2.7.3

Repeat table 14.3.1.2 for Treatment-Emergent Adverse Events with frequency higher in GSP 301 NS group than in Placebo NS group

Programming note: for table 14.3.1.11, 14.3.1.12, 14.3.1.13 and 14.3.1.14, frequency for each event is determined by No of subjects that has that event divided by number of subject in the treatment group.

Table 14.3.1. 15 Overall Summary of Adverse Events during Placebo Run-in Period (Run-in Set)

Source: Listing 16.2.7.2

Repeat table 14.3.1.1 for adverse events that occurred in the placebo run-in period, overall column only

Table 14.3.1. 16 Overall Summary of Adverse Events Pre-run-in (All Subjects)

Source: Listing 16.2.7.3

Repeat table 14.3.1.1 for adverse events that occurred in the Pre-run-in Period, overall column only

Table 14.3.2.1.1 Summary of Vital Signs (Safety Analysis Set)

Parameter: Systolic Blood Pressure (mmHg)

Visit	Placebo NS (N=xxx)		GSP 301 NS (N=xxx)	
	Actual Value	Change from Baseline[a]	Actual Value	Change from Baseline[a]
Screening				
n (%)	xx (xx)		xx (xx)	
Mean (SD)	xx.x (xx.xx)		xx.x (xx.xx)	
Median	xx.x		xx.x	
Min, Max	xx, xx		xx, xx	
Baseline				
n (%)	xx (xx)		xx (xx)	
Mean (SD)	xx.x (xx.xx)		xx.x (xx.xx)	
Median	xx.x		xx.x	
Min, Max	xx, xx		xx, xx	
Day 8				
n (%)	xx (xx)	xx (xx)	xx (xx)	xx (xx)
Mean (SD)	xx.x (xx.xx)	xx.x (xx.xx)	xx.x (xx.xx)	xx.x (xx.xx)
Median	xx.x	xx.x	xx.x	xx.x
Min, Max	xx, xx	xx, xx	xx, xx	xx, xx
Repeat Day 8 for Day 15/Early Termination				

Source: Listing 16.2.8.5

SD = Standard Deviation; Max=maximum; Min=minimum; N= number of subjects in the SAS treatment group; n= number of subjects with data available, percentages are based on N.

Baseline is defined as the value collected at Randomization Visit 2.

[a] Change from baseline: post-baseline value – baseline value. For the change from baseline, only subjects with a value at both baseline visit final/discontinuation visit are included.

Program: xxxx.sas Executed: DDMMYYYY HH:MM

Page X of Y

Programming Note: Repeat table for all VS parameters: diastolic blood pressure (mmHg), pulse rate (BEATS/MIN), height (cm) and weight (kg). Note that height and weight are only collected at baseline and Day 15/Early Termination.

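### The treatment-emergent AE definition has no worsening clause, so whether a run-in event that worsens on randomised drug is counted by arm depends on how the site records it

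*SAP*

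**What the plan says.** After screening, all subjects go through a "single-blind, placebo run-in period for 7 to 10 days" (Protocol 6.1). AEs are collected from consent onwards (Protocol 11.4.1), so run-in events are on record before the first randomised dose.

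SAP 9.2.1 defines treatment emergence by timing: "Adverse events occurring after the first dose of the randomized study medication will be defined as treatment-emergent adverse events (TEAEs". Protocol 13.8.3 is equivalent: "Adverse events occurring after the first dose of study medication will be defined as TEAEs". Neither sentence mentions an event that began earlier and got worse.

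Other rules place events by when they started:

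- SAP 9.2.1 on the treatment arm: "Events will be assigned to the study treatment administered prior to the start of the TEAE".
- SAP 9.2.1 on run-in events: "Any AE that occurs during the placebo run-in period will be summarized separately from the AEs occurring during the randomized treatment period". The shell of Table 14.3.1.15 reads: "Repeat table 14.3.1.1 for adverse events that occurred in the placebo run-in period, overall column only".
- Protocol 13.8.3 calls events before the first randomised dose "pre-treatment AEs and included in the subject listings but not in the summary tables". Protocol 13.8.2 does have run-in AEs summarised separately, so those two sections also differ.

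The protocol's definition of an AE is wider than onset. Section 11.2.1 covers a "symptom or disease (new or exacerbated", and section 11.1 has clinically significant assessments that worsen from baseline recorded as AEs. Sections 11.4.1 and 11.4.2 cover follow-up to resolution and updating a record when a diagnosis becomes available. They say nothing about a change in severity.

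**The concern.** The secondary objective is the safety and tolerability of the randomised spray. The run-in spray is the same vehicle without the active drugs, and events such as epistaxis, nasal irritation, headache or cough could begin during it. In the sponsor's 52-week study in older subjects, 7.1% of those on the pH 3.7 placebo had treatment-related events (Protocol 4.4), and SAP 4.2 gives pH 3.7 for this trial's placebo. That figure comes from a longer study in an older population and is not a run-in rate, but it makes vehicle-related events plausible.

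Suppose a mild run-in event becomes moderate or severe after randomisation and the site updates the existing record. The onset date then still lies in the run-in. Read literally, the plan sends the event to a table without treatment columns and may leave it out of the by-arm tables of treatment-emergent events, including those by severity, by relationship and for discontinuation. Another site that opens a new record for the same worsening has it counted. The arm comparison then rests partly on a recording habit that neither document fixes.

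**Working it through.** This is a question of definition, so the first step is to follow one event through the text: mild epistaxis starting in the run-in and becoming moderate after the first randomised dose.

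| Step | Worsening entered as a new AE | Worsening kept on the run-in record |
|---|---|---|
| Allowed by the protocol? | Yes: 11.2.1 includes exacerbation, and its exclusions cover only pre-existing conditions that do not worsen | Not ruled out: 11.4.1 and 11.4.2 give no instruction |
| Start date | After the first randomised dose | In the run-in |
| Treatment-emergent under SAP 9.2.1? | Yes | Not on a reading by onset |
| Tables by arm (14.3.1.2, 14.3.1.3, 14.3.1.5, 14.3.1.6) | Counted | May be missed |
| Discontinuation tables (14.3.1.4, 14.3.1.10) | Counted if it leads to withdrawal | May be missed, because these shells are limited to treatment-emergent events |
| Where it does appear | Treatment-period listing and tables | Run-in listing and pooled Table 14.3.1.15 |

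The shell of Listing 16.2.7.1 carries one start date, one end date and one severity per event. That fits either column, since a worsening could be a second row.

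The second step is size. The plan has no figure for run-in AEs or for the share that worsen, so there is nothing of its own to reproduce on this point. The only input from the documents is the planned arm size: 382 / (1 − 0.15) = 449.4, rounded up to 450, or 225 per arm. The other two inputs are assumptions:

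- r, the share of randomised children with a run-in AE: 2% to 15%.
- w, the share of those whose event worsens on randomised treatment: 5% to 20%.

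Children affected per arm = 225 × r × w, if every worsening stays on its run-in record.

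| r | w | 225 × r × w | % of 225 |
|---|---|---|---|
| 2% | 5% | 0.2 | 0.1% |
| 5% | 10% | 1.1 | 0.5% |
| 10% | 10% | 2.25 | 1.0% |
| 10% | 20% | 4.5 | 2.0% |
| 15% | 20% | 6.75 | 3.0% |

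These are counts across all event terms together. The 1%, 2% and 3% display cut-offs of Tables 14.3.1.11 to 14.3.1.13 correspond to 2.25, 4.5 and 6.75 of 225 children, but the programming note applies them to each event separately. The totals above would be spread over several terms and should not be set directly against those cut-offs.

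The third step is the arm difference. With the same w in both arms, the expected number missed is equal and the expected absolute difference is unchanged. In the most extreme corner of the assumed ranges (r = 15%, w = 20% in one arm and 5% in the other), the missed counts are 6.75 and 225 × 0.15 × 0.05 = 1.69. The missed difference is 5.1 children, or 2.25 percentage points. With r = 2% and the same w values it is 0.9 − 0.225 = 0.7 children.

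**The case against.** The strongest reply is that the definitions nest. The rule for treatment emergence applies to AEs, and an exacerbation is itself an AE under Protocol 11.2.1. A worsening after the first randomised dose is then an AE occurring after that dose and is already treatment-emergent. The case report form and any completion instructions, which are not in these documents, may settle the recording question. This part stands to the extent that a reader may not infer that such events are absent from every treatment-arm table. It does not remove the gap: the protocol permits a new record but does not require one.

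There are also backstops by arm:

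- Tables 14.3.2.3.1 and 14.3.2.3.2 give ENT grades by visit and arm, with baseline at Visit 2 after the run-in.
- Table 14.1.1 counts terminations for an adverse event by arm whatever the onset.
- SAP 9.2.3 promises SAEs and AEs leading to discontinuation by treatment group without a treatment-emergent limit.
- Randomisation criteria 1, 3 and 8 keep out children whose AE altered eligibility and those with recent respiratory infections.

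These are real but partial. The ENT tables do not follow the individual child, since SAP Table 6 plans shift tables only for vital signs, and they do not cover headache or cough. The shells of Tables 14.3.1.4 and 14.3.1.7 are narrower than the text of SAP 9.2.3.

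A reader might also infer that the loss works in favour of the active spray. The documents do not support that. The rule is the same in both arms, and nothing in them says that worsening is more frequent on either.

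**Conclusion.** The gap is real and worth closing before database lock. Treatment emergence is defined by timing alone in both documents, and neither says how a run-in AE that worsens is recorded and classified. Such an event may be missed in the by-arm treatment-emergent tables, or it may be counted, depending on the site. It is not lost altogether, because all AEs are listed.

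The size is unknown. Under the stated assumptions it runs from negligible to a few children per arm, and the upper end requires every worsening to stay on its run-in record. Even then, a child who also has another treatment-emergent event still counts in the row for any event. An arm difference is diluted only if worsening differs between the arms. If nothing worsens, or every site opens a new record, nothing is missed.

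**What to change.** 1. In SAP 9.2.1 and Protocol 13.8.3, define a treatment-emergent AE as one that starts on or after the first randomised dose, or that starts earlier and increases in severity or becomes serious on or after that dose. Apply this to all treatment-emergent tables.
2. In Protocol 11.4.2, state that such a worsening is entered as a new AE record with the date of worsening. Without a dated record, the programming cannot identify it later.
3. Align the shells of Tables 14.3.1.4 and 14.3.1.7 with the text of SAP 9.2.3, so that it is clear whether SAEs and AEs leading to discontinuation are limited to treatment-emergent events.

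The cost is one sentence in each document, one line of recording instruction, one programmed flag and two shell edits. Treatment-emergent counts may rise slightly in both arms.
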